7.4 Main Study Visit(s)

All participants will return for the study-related blood draws on Days 1, 3, $7(\pm 1)$, $14(\pm 2)$, $30(\pm 7)$ 180 (± 14) and year 2-3.5 (optional visit) after immunization. These visits will last approximately 20 minutes.

On days 1, 3, 7, 14, 30 and 180 study personnel will review current health status including:

- Evaluation of local REs and systemic REs of grade 3 or higher severity developing after the last visit (only until Day 7 Visit).
- Any adverse event (AE) that limited self-care activities of daily living or serious adverse event (SAE) which may not have been reported by the participant by calling the site as directed at a prior visit.
- Any medications administered after vaccination.

At the end of the visits on days 1, 3 and 7, 14 and 30 the participant will be instructed to promptly call the site if he/she becomes sick or has been treated at the doctor's office or emergency department or has been hospitalized for any illness throughout D180 of the study. The participant will also be instructed to call the site if he/she develops any adverse event that limits self-care activities of daily living even if he/she decides not to get medical care, or starts/stops any medications/therapies.

Refer to section 8.2.5 for safety data that must be recorded and reported.

A focused physical exam will be conducted -if indicated- based on results of the review of health status as above.

At year 2-3.5 visit, participant will be asked about any major change in health status and if they have received any pneumococcal vaccine since last study visit.

7.5 Follow-up Visit(s)

Please refer to 7.4

7.6 Visit Windows

Study visits should take place within the time limits below:

D0, D1, D3, D7 (+1), D14 (+2), D30 (+7), D180 (+14) and year 2-3.5

7.7 Study Procedures

Refer to sections 7.3 and 7.4

7.8 Study Arm Assignment Procedures

7.8.1 Blinding and Randomization

In this study 88 healthy subjects 22 subjects (ages 25-40) and 66 subjects (ages 60-89)) will be randomized to receive PPV23 or PCV13 in a 1:1 ratio.

The randomization of the pre-filled vaccine syringes will be performed by the Emory Investigational Drug Service.

7.8.2 Securing Randomization Information

The information on and randomization is kept at the Emory Investigational Drug Service.

7.8.3 Requirements for Unblinding

HIPC: VAX-003 is an open study. Subjects will be made aware of which vaccine they are receiving at the time of vaccine administration and will be informed about:1. the need for a second dose of vaccine depending on age at entry and randomization status.2. the commitment of the investigators to inform subjects if any changes in recommendations for revaccination develop during subject's participation in the study.

7.8.4 Documenting an Unblinding

N/A

8. SAFETY PROCEDURES

8.1 Stopping Rules

8.1.1 Study Stopping Rules

Study enrollment will be suspended pending expedited review of all pertinent data by the institutional review board, the ISM, and the NIAID, if any of the following occurs:

- One unexpected SAE related to the vaccination
- Two unexpected AEs of grade 3 or higher severity of similar nature related to the vaccination
- Study vaccine is recalled by the manufacturer
- Occurrence of a case of Guillain-Barré Syndrome, radiculoneuropathy, anaphylactoid reaction, anaphylaxis or serum sickness considered related to vaccination

8.1.2 Individual Stopping Rules

Individual stopping rules include:

• Failure to receive a full dose of vaccine.

8.1.3 Follow-up after early study termination

Participants who are prematurely terminated from the study due to a related AE/SAE will be followed until resolution of the AE or until 30 days after a participant terminates from the study, whichever comes later.

Note:

Resolution of an AE is defined as the return to baseline status or as stabilization of the condition with the expectation that it will remain chronic.

8.1.4 Participant Replacement

Up to the discretion of the PI, participants receiving concomitant medications may still continue with scheduled study blood draws. Subjects receiving concomitant medications, along with participants with early termination from this study for any reason, may be replaced as needed to preserve the statistical power needed to prove the primary endpoint (Refer to section 9.1).

8.2 Adverse Events

This section defines the types of adverse events and outlines the procedures for appropriately collecting, grading, recording, and reporting them. Information in this section complies with ICH Guideline E2A: Clinical Safety Data Management: Definitions and Standards for Expedited Reporting and ICH E6: Guideline for Good Clinical Practice, and applies the standards set forth in the National Cancer Institute (NCI), Common Terminology Criteria for Adverse Events Version 4.0 [Published: May 28, 2009; revised version 4.03; June 14. 2010)]. These criteria have been reviewed by the study investigators and have been determined appropriate for this study population.

8.2.1 Definitions

8.2.1.1 Adverse Events

An adverse event (AE) is any occurrence or worsening of an undesirable or unintended sign, symptom, laboratory finding, or disease that is experienced during participation in the trial. An AE can therefore be any unfavorable and unintended sign, symptom, or disease temporarily associated with the use of a medicinal (investigational) Study Agent(s)/Intervention(s), whether or not related to the medicinal (investigational) Study Agent(s)/Intervention(s).

8.2.1.2 Adverse Events Associated with Study Vaccines and Study Procedures

The most common adverse reactions after vaccine administration are fully described in Section 1.6.1.

Adverse events after blood draws may include:

- Fainting /Vasovagal events
- Bruising at puncture site larger than 2 cm diameter
- Bleeding from puncture site lasting more than 30 minutes
- Swelling at puncture site larger than 2 cm

8.2.2. Serious Adverse Event (SAE)

An adverse event or suspected adverse reaction is considered "serious" if, in the view of either the investigator or sponsor, it results in any of the following outcomes:

-Death

- A life-threatening adverse event

- Inpatient hospitalization or prolongation of existing hospitalization

- A persistent or significant incapacity or substantial disruption of the ability to conduct normal life functions

-A congenital anomaly/birth defect

Important medical events that may not result in death, be life-threatening, or require hospitalization may be considered serious when, based upon appropriate medical judgment, they may jeopardize the patient or subject and may require medical or surgical intervention to prevent one of the outcomes listed in this definition.

Examples of such medical events include allergic bronchospasm requiring intensive treatment in an emergency room or at home, blood dyscrasias or convulsions that do not result in inpatient hospitalization, or the development of drug dependency or drug abuse.

Note:

An adverse event or suspected adverse reaction is considered "life-threatening" if, in the view of either the investigator or sponsor, its occurrence places the patient or subject at immediate risk of death.

It does not include an adverse event or suspected adverse reaction that, had it occurred in a more severe form, might have caused death.

8.2.3. Unexpected Adverse Event or Adverse Reaction

An adverse event or suspected adverse reaction is considered "unexpected" if it is not listed in the product label information of PNEUMOVAX®23 nor PRENAR®13 or is not listed at the specificity or severity that has been observed.

For example, under this definition, hepatic necrosis would be unexpected (by virtue of greater severity) if the investigator brochure referred only to elevated hepatic enzymes or hepatitis. Similarly, cerebral thromboembolism and cerebral vasculitis would be unexpected (by virtue of greater specificity) if the investigator brochure listed only cerebral vascular accidents.

"Unexpected," as used in this definition, also refers to adverse events or suspected adverse reactions that are mentioned in the product label information as occurring with a class of vaccine or as anticipated from the pharmacological properties of the product but are not specifically mentioned as occurring with the particular drug under investigation.

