8.2.7. SAE Reporting Criteria and Procedures

The Principal Investigator will be notified by the study staff as soon as a staff member becomes aware of the SAE. In the absence of the Principal Investigator, a physician sub-investigator will be notified.

8.2.7.1. Notifying the Independent Safety Monitor and the NIAID Medical Officer of SAEs and pregnancy

The Principal Investigator will notify the ISM and the NIAID Medical Officer by email simultaneously of any related SAE within 24 hours of becoming aware of the event.

The investigator will be informed immediately of any pregnancy and will report all pregnancies within 24 hours to the ISM and the NIAID Medical Officer utilizing the SAE report form. This report is for tracking purposes only. All pregnancies that are identified during the study will be followed to conclusion and the outcome of each will be reported. The investigator will discuss with the participant and/or the treating physician the known possible risks of the investigational product(s) on the fetus. Monitoring of the participant will continue until the conclusion of the pregnancy, and a follow-up SAE report form detailing the outcome of the pregnancy will be submitted to the NIAID Medical Officer and Project Manager. Subject will not be terminated from the study if pregnancy occurred after day 30.

The investigator will also report within 24 hours to the ISM and the NIAID Medical Officer any of the following events:

- Guillain-Barré Syndrome
- Radiculoneuropathy
- Anaphylactoid reactions
- -Anaphylaxis

- Serum Sickness

For non-related SAEs, the Principal Investigator will notify the ISM and the NIAID Medical Officer by email simultaneously of any related SAE within 7 days of becoming aware of the event.

The initial SAE CRF should be signed by the PI or co-PI and include as much information as possible. The SAE case report form will re-submitted and signed by the PI or co-PI to the ISM the NIAID Medical Officer with updated relevant medical information as needed until the event is considered closed by the ISM and the NIAID Medical Officer.

The study biostatistician, PI or study data manager will provide the ISM and the NIAID Medical Officer with cumulative periodic safety reports (tables and data listings of all AEs, including SAEs) during the conduct of the study. Resulting memorandums following evaluations of safety data will be sent to the IRB as needed in accordance with IRB rules and regulations.

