8.3. Protocol Deviations

Deviations occur when the Investigator, site study staff, or participants fail to adhere to protocol requirements or when there is non-adherence to (GCP) as delineated in ICH E6 (R1) guidelines. NIAID will not allow any waivers or planned deviations from the protocol.

Upon determination that a protocol deviation has occurred, the study staff will a) notify the Principal Investigator, b) notify the NIAID Project Manager(refer to investigator's signature

page for contact information) and c) will complete the Protocol Deviation form. NIAID may request discussion with the Principal Investigator and the ISM to determine the effect of the protocol deviation on the study participant and his/her further study participation, the effect of the protocol deviation on the overall study and corrective actions.

The Principal Investigator will complete and sign the Protocol Deviation form and submit it to the NIAID Medical Officer and Project Manager, to the ISM Monitor and to the site IRB, per IRB regulations.

Identification of protocol deviations will be done through the quality manager at the study site, or the NIAID project manager and/or Medical Officer. Reviewing and reporting of minor protocol deviations will be discussed at the Hope Clinic monthly meetings and among the Hope Clinic investigators. Major protocol deviations will be discussed with the PI, the ISM and NIAID study teams and will be promptly communicated to the regulatory agencies as needed.

All study deviations will be captured in monthly reports along with safety data and forwarded to the study sponsor and the ISM.

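### Expectedness is judged against both vaccine labels together, so a related event listed only for the vaccine not received cannot set off two of the four enrolment-pause triggers

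*Combined protocol and SAP*

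**What the plan says.** The protocol defines an unexpected event in section 8.2.3, in two places.

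- The first paragraph has two limbs. An event is unexpected "if it is not listed in the product label information of PNEUMOVAX®23 nor PRENAR®13", or if it "is not listed at the specificity or severity that has been observed".
- The third paragraph adds events that a label mentions for the vaccine class, or as foreseeable from the pharmacology, but that are "not specifically mentioned as occurring with the particular drug under investigation".

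Section 8.1.1 gives four triggers that suspend enrolment until an expedited review is done. Two use the defined word: "One unexpected SAE related to the vaccination" and "Two unexpected AEs of grade 3 or higher severity of similar nature related to the vaccination". The other two do not: a manufacturer's recall, and a vaccine-related case of any of five named conditions (Guillain-Barré syndrome, radiculoneuropathy, anaphylactoid reaction, anaphylaxis, serum sickness).

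Reporting is separate from pausing. Section 8.2.7.1 requires notice to the independent safety monitor and the NIAID Medical Officer of "any related SAE within 24 hours of becoming aware of the event", with no condition on expectedness.

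**The concern.** Each participant is randomized to one of two different products, a plain polysaccharide vaccine or a conjugate vaccine. Whether an event is a surprise should depend on what is known about the product given. The definition instead names both labels and asks whether the event is on neither. Knowledge about one vaccine can then make an event expected after the other.

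What is at stake is the automatic pause. With thresholds of one and two events, the coding of a single event can decide whether enrolment stops for review.

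**Working it through.** No figure is stated for the stopping rules, so there is nothing to reproduce. The check is one of logic and counting.

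**Step 1: the first limb.** Each event is either listed or not on the label of the vaccine received, and either listed or not on the other label. The rule as written makes an event unexpected only when both are no. A vaccine-specific rule looks only at the label of the vaccine received.

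| On label of vaccine received | On other label | Rule as written | Vaccine-specific rule |
|---|---|---|---|
| No | No | Unexpected | Unexpected |
| No | Yes | **Expected** | **Unexpected** |
| Yes | No | Expected | Expected |
| Yes | Yes | Expected | Expected |

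The rules differ in one of the four combinations. It can arise in either arm.

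**Step 2: do the other limbs close the gap?** The severity and specificity limb names no particular label. If the other label lists the event as it was observed, this limb does not make it unexpected. The third paragraph covers class effects and pharmacologically foreseeable effects. An event listed outright for the other study vaccine is neither.

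**Step 3: count the triggers.** Section 8.1.1 has 4 triggers and 2 use the word unexpected. The first needs 1 event and the second needs 2 of similar nature. For an event in the second row of the table that is not one of the five named conditions, neither trigger fires.

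**Step 4: what remains for such an event.**

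- *Related SAE:* the 24-hour notice in section 8.2.7.1 still applies. The automatic pause is lost; the notification is not.
- *Related, non-serious, grade 3:* section 8.2.7.1 gives no 24-hour notice outside the five conditions. The stated routes are the periodic cumulative safety reports in that section and, under section 8.3, deviations "captured in monthly reports along with safety data and forwarded to the study sponsor and the ISM".

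**Step 5: is such an event plausible?** Section 1.6.1 lists seizure and cellulitis among the post-approval reactions for the polysaccharide vaccine. The protocol's text on the conjugate vaccine mentions neither, and neither is one of the five named conditions. Section 8.2.2 gives convulsions without hospitalization as an example of an event that may be serious. This is only an illustration: the protocol's text on the conjugate vaccine describes solicited reactions and gives no post-marketing list, so silence there does not show that the full label is silent.

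**The case against.** The strongest reply is that naming both labels may be loose drafting for whichever label applies. The third paragraph of section 8.2.3 speaks of one particular drug, and section 8.2.4 has the safety monitor weigh events against the known profile of the study product, in the singular. That may well be the intent. But both vaccines are under investigation, and neither passage says that listing on the other label is to be ignored. If the intent is vaccine-specific, the first paragraph should say so.

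The other objections concern size, and they largely stand.

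- No affected event can be shown from the documents.
- Both triggers need an SAE or a grade 3 event. Where a label lists a term without a grade, a severe case may already count as unexpected through the severity limb.
- The safety monitor reviews adverse events generally under section 8.2.4 and can advise on continuing the study whatever the expectedness code.
- A pause protects only people not yet vaccinated. Section 7.1 plans 88 participants over about 18 months. With even accrual that is 88 / 18 = 4.9 per month, or 4.9 / 2 = 2.4 per arm. A month's delay would expose two or three more people in that arm to a licensed vaccine.

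These points limit the consequence. They do not correct the rule.

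**Conclusion.** The concern holds as a point of wording with a modest safety consequence. Taken literally, the definition lets a related event listed only for the other vaccine count as expected, and so disables 2 of the 4 pause triggers for that event. This assumes that the first paragraph is applied as written and that at least one relevant event is on only one label, at the severity and specificity observed. If both labels list the same events, the effect is nil. The documents give neither the full labels nor rates for such events, so no probability of a missed pause can be supported. No endpoint, sample size or analysis is affected.

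**What to change.** Reword the first paragraph of section 8.2.3 along these lines: *An event is unexpected if the label of the study vaccine given to that participant does not list it, or does not list it with the severity or specificity seen.* Tell those completing the CRF to code expectedness on that basis. The third paragraph and the triggers in section 8.1.1 can stay as they are.

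The cost is one sentence and a line of CRF guidance. The dispensing log in section 5.4 already records which vaccine each participant received, section 8.2.5.1 already makes expectedness a CRF item, and section 7.8.3 confirms that the study is open. The drawback is possibly a few more pauses for review. These could include pauses for SAEs judged unlikely to be related, because section 8.2.6.2 places that code among the related categories.

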8.2.4. Independent Safety Monitor

The ISM is a physician with relevant expertise whose primary responsibility will be to provide independent safety monitoring in a timely fashion and to provide recommendations regarding the safe continuation of the study.

The ISM is a physician independent from the study team and will evaluate adverse events, including SAE, against the known safety profile of the study product to assess for possible changes to the overall risk of the study. Contact information for the ISM and the NIAID Medical Officer is listed in page 3 of this protocol.

The ISM and the NIAID Medical Officer will communicate as needed to discuss any safety events of special interest developing during the study and when conducting the review of periodic reports of cumulative safety data. The study has provisions for a back-up to ensure that independent safety monitoring happens at all times during the study. Additional roles and responsibilities of the ISM are described in sections 8.2.7 and 8.3 below.

8.2.5 Collecting, Recording and Managing Adverse Events

8.2.5.1 Collecting and reporting Adverse Events

Adverse events occurring after the subject has signed the consent will be collected and reported as follows:

- Any Adverse Event (including but not only- vaccine reactions and local or systemic Reactogenicity Events) of grade 3 or higher severity or SAE occurring after vaccination while the subjects is still at the clinical site.
- Local REs and systemic REs of grade 3 or higher severity occurring from Day 0 to Day 7 reported over the telephone by the participant and/or assessed at the clinic.
- AEs of grade 3 or higher severity throughout D180 of the study (including -but not only

 AEs linked to blood draws).
- All SAEs throughout D180.

Adverse events may be identified during this study through any of these methods:

- 1. Examination of the participant during study visits.
- 2. Questioning the participant during study visits.

3. Receiving a safety report from the participant by phone or during a site visit at any time during the study

Note: Not all safety events identified may require recording and reporting

A complete recording of safety events in the CRF will include event term, date of onset and resolution/stabilization, assessment of severity, relationship to study vaccine or procedures/intervention(s) such as phlebotomy, expectedness, determination of whether the AE qualifies as serious, treatment required, action taken with study participation and outcome. AEs qualifying as SAEs also require a narrative of the event. Updates in safety events will be recorded as additional information becomes available.

8.2.5.2 Managing Adverse Events

The site investigator must apply his or her clinical judgment as to whether an AE is of sufficient severity to require that the participant immediately be removed from further treatment under the protocol. The investigator must institute any necessary medical therapy to protect a participant from any immediate dangers.

Severe related AEs and all SAEs will be followed until they are resolved.

Participants who are prematurely terminated from the study due to a safety event will be followed until resolution of the AE or until 30 days after a participant terminates from the study, whichever comes later.

Note:

Resolution of an AE is defined as the return to baseline status or as stabilization of the condition with the expectation that it will remain chronic.

8.2.6. Grading and Attribution

8.2.6.1. Grading criteria

Adverse events requiring reporting in this study will be graded according to the criteria set forth in the National Cancer Institute's Common Terminology Criteria for Adverse Events (Version 4.03; June 14, 2010).

Adverse events requiring reporting in this study if not listed in the NCI-CTCAE (Version 4.03; June 14, 2010) will be graded on a scale from 1 to 5 according to the following general guideline in the NCI-CTCAE manual):

Grade 1 Mild; asymptomatic or mild symptoms; clinical or diagnostic observations only; intervention not indicated.

Grade 2 Moderate; minimal, local or noninvasive intervention indicated; limiting ageappropriate instrumental ADL*.

Grade 3 Severe or medically significant but not immediately life-threatening;

hospitalization or prolongation of hospitalization indicated; disabling;

limiting self-care ADL**.

Grade 4 Life-threatening consequences; urgent intervention indicated.

Grade 5 Death related to AE.

*Instrumental Activities of Daily Living (ADL) refer to preparing meals, shopping for groceries or clothes, using the telephone, managing money, etc.

**Self-care Activities of Daily Living (ADL) refer to bathing, dressing and undressing, feeding self, using the toilet, taking medications, and not bedridden.

Anaphylaxis is a disorder characterized by an acute inflammatory reaction resulting from the release of histamine and histamine-like substances from mast cells, causing a hypersensitivity immune response. Clinically, it presents with breathing difficulty, dizziness, hypotension, cyanosis and loss of consciousness and may lead to death.

Severity grading of anaphylaxis as per the NCI-CTCAE (Version 4.03; June 14, 2010) manual is as follows:

Grade 1=

Grade 2=

Grade 3= Symptomatic bronchospasm, with or without urticaria; parenteral intervention

indicated; allergy-related edema/angioedema; hypotension

Grade 4= Life-threatening consequences; urgent intervention indicated

Grade 5= Death

